12.2 Hormonal Contraceptives

Pexidartinib has been indicated to be a moderate CYP3A4 inducer, as concurrent administration of pexidartinib decreased the $AUC_{0-\infty}$ of the CYP3A4 substrate midazolam by 57%. As the hormonal contraceptive ethinyl estradiol is a CYP3A4 substrate, there is a potential that exposure of ethinyl estradiol may decrease on concurrent administration with pexidartinib. As pexidartinib may cause embryo-fetal harm when administered to a pregnant woman, females of reproductive potential should be advised to use an effective, non-hormonal method of contraception during treatment with pexidartinib and for one month after the last dose. Males with female partners of reproductive potential should be advised to use an effective method of contraception during

treatment with pexidartinib and for one month after the last dose. Female partners of male patients should concurrently use effective contraceptive methods (hormonal or non-hormonal).

12.3 Acid-reducing Agents

Avoid the concomitant use of proton pump inhibitors (PPIs) while taking pexidartinib. As an alternative to a PPI, administer pexidartinib 2 hours before or 2 hours after taking a locally-acting antacid, or if using a histamine 2 (H₂)-receptor antagonist, administer pexidartinib at least 2 hours before or 10 hours after taking an H₂-receptor antagonist.

13.0 PROCEDURES (DOSE ESCALATION COHORTS)

13.1 Screening Evaluation

Within 21 days (28 days for the one-week run-in patients) before test article administration on study C1D1 (28 days for assessment of tumor burden), all patients will have a screening evaluation that includes the following:

1. Sign and date an IRB/IEC-approved informed consent form before any study-specific screening procedures are performed.
2. Medical history including ethnic origin (Hispanic or non-Hispanic) and race (white, black, Asian, or other).
3. Physical examination including weight (kg) and height (cm).
4. Vital signs (sitting blood pressure, pulse rate, and respiratory rate, and oral temperature [°F]).
5. Standard 12-lead ECG (in triplicate 2 minutes apart) to determine the mean QTc, which must be <450 msec).
6. Recording of concomitant medications.
7. Clinical laboratory evaluation (hematology, chemistry, coagulation, urinalysis, TSH, serum pregnancy test (women of child-bearing potential); see [Attachment 1](#)).
8. ECOG Performance status assessment.
9. Baseline assessment of tumor burden (see [Attachment 4](#)).
10. Tumor biopsy and/or FDG-PET scan [OPTIONAL].

A patient who meets all of the inclusion criteria will be assigned a patient number. Each patient should fast for 1 hour before and 1 hour after test article administration.

13.2 Run-In Period (Selected Cohorts) – Cycle 1 Day(-7), Day(-6), and Day(-4)

1. All 3 days: Recording of concomitant medications and adverse events.

2. All 3 days: Vital signs (sitting blood pressure, pulse rate, and respiratory rate and oral temperature [°F]).
3. All 3 days: Pre-dose blood sample collection for PK analysis and response biomarkers.
4. C1D(-7): Post-dosing blood collection for PK analysis.

13.3 Pre-Treatment (Baseline): Cycle 1 Day 1

Patients will return to the clinic on C1D1 and will undergo the following procedures:

1. Recording of concomitant medications.
2. Vital signs (sitting blood pressure, pulse rate, and respiratory rate and oral temperature [°F]).
3. Standard 12-lead ECG in triplicate 2 minutes apart.
4. Pre-dose blood sample collection for PK analysis and response biomarkers.
5. Pre-dose morning urine collection for response biomarkers.

13.4 Post-Treatment: Cycle 1 Day 1 and Cycle 1 and Day 2

On C1D1, each patient will receive the assigned dose of test article. AE monitoring will be continuous. Vital signs, ECGs, laboratory evaluations, and PK sample collections will be completed at designated times during the study (see [Trial Flow Charts](#)). The blood sample for PK analysis should be collected at the scheduled time, within the windows noted in the PK section. ECG in triplicate will be repeated at 2, 4, and 6 hours after administration of study drug. Pulse and blood pressure will be repeated at 1 and 4 hours post administration of study drug on C1D1. Patients will return to the clinic on the morning of C1D2 prior to dosing on that day for evaluation and blood draw to obtain the predose PK time-point (approximately 12 hours after the previous evening dose for a BID dosing regimen).

13.5 Cycle 1 Day 8 ± 1 Day

Patients will return for evaluation of AEs, concomitant meds, vital signs, physical exam, clinical laboratory values, and collection of serum and morning urine for biomarker assessments. A predose blood sample for PK and as well as predose blood samples for response biomarkers will be obtained, as well as a predose morning urine for response biomarkers (see [Trial Flow Charts](#), pp. 16–20).

13.6 Cycle 1 Day 15 and Cycle 1 Day 16 (± 2 Days)

At the C1D15 visit, AEs, concomitant meds, vital signs, physical exam, and clinical laboratory values will be recorded. Triplicate ECGs will be obtained 2, 4, and 6 hours postdose, and PK

evaluation performed as on C1D1 (see [Trial Flow Charts](#), pp. 16–20). Patients will return to the clinic on the morning of C1D16 prior to dosing on that day for evaluation and blood draw to obtain the predose PK time-point (approximately 12 hours after the previous evening dose for a BID dosing regimen). An on-treatment tumor biopsy and/or FDG-PET scan may be obtained in selected patients.

13.7 Cycle 2 Day 1 (\pm 7 Days)

On C2D1, evaluations will consist of AEs, concomitant meds, physical exam with vital signs, ECOG performance status assessment, clinical laboratory values, a predose PK time-point, serum/urine collection for biomarkers, and blood collection for circulating tumor cells.

13.8 Continued Dosing

Pexidartinib, at the assigned dose, will be offered to each patient as long as both the patient and investigator agree that it continues to be well tolerated, and there has been no evidence of disease progression. Study visits will occur at approximately 4 week (\pm 7 days) intervals for assessment of safety (AEs, concomitant meds, physical exam with vital signs, and clinical laboratory values), PK, and ECOG status, and 8 week (\pm 7 days) intervals (or as clinically indicated) for assessment of tumor response or progression. In addition, in the dose escalation phase, hematology (CBC with differential) will be measured every two weeks after Cycle 1. The mid-cycle values may be provided from a local laboratory.

13.9 Dose Modification (Dose Escalation Cohorts)

Reduction/interruption of dosing for adverse events may take place any time. Below are general guidelines for dosage modification for pexidartinib-related toxicities as well as guidelines for their management.

For toxicities which are considered by the investigator unlikely to develop into serious or life-threatening events (e.g., alopecia, altered taste, etc.), treatment should be continued at the same dose without reduction or interruption. In addition, if any Grade 1 toxicity occurs, treatment should be continued at the original dose without interruption. If drug-related Grade 2 toxicity occurs, the Sponsor should be notified, and the investigator may discontinue or interrupt treatment with pexidartinib if it is considered to be medically appropriate. If dosing is interrupted, treatment at the same dose may be resumed once toxicity is \leq Grade 1.

If Grade 3 or 4 drug-related toxicity occurs, immediate treatment interruption will be followed by a selective dose reduction depending on the types of toxicity, and based on discussion and agreement between the investigator and Sponsor after recovery of the toxicity to at least Grade 1. pexidartinib re-challenge after interruption of dosing may occur only if the investigator and Sponsor agree that it is in the best interest of the patient. In addition, the patient's ECOG performance status must be 0–2. Following re-challenge at a modified dose, study visits will occur at approximately one month intervals for assessment of safety and PK, and two month

intervals for assessment of tumor response or progression. Dosing interruptions longer than 3 weeks should generally result in discontinuation from the study, unless the patient has demonstrated a clinical benefit from therapy and would like to continue dosing with study drug. All adjustments should be made in consultation with the Medical Monitor.

If treatment with pexidartinib is interrupted due to bone marrow toxicity in Cycle 2 and beyond, growth factors may be used. However, growth factors should not be used concomitant with study drug dosing, as it will interfere with the assessment of drug toxicity.

14.0 PROCEDURES (EXTENSION COHORTS)

14.1 Screening Evaluation

Within 21 days before test article administration on study C1D1 (28 days for assessment of tumor burden), all patients will have a screening evaluation that includes the following:

1. Sign and date an IRB/IEC-approved informed consent form before any study-specific screening procedures are performed.
2. Medical history including ethnic origin (Hispanic or non-Hispanic) and race (white, black, Asian, or other).
3. Physical examination including weight (kg) and height (cm). Vital signs (sitting blood pressure, pulse rate, and respiratory rate, and oral temperature [$^{\circ}$ F]).
4. Standard 12-lead ECG to determine the QTcF, which must be <450 msec (for males) or <470 msec (for females).
5. Recording of concomitant medications.
6. Clinical laboratory evaluation (hematology, chemistry, urinalysis, serum pregnancy test (women of child-bearing potential)
7. ECOG Performance status assessment.
8. Baseline assessment of tumor burden (see [Attachment 4](#)).
9. Obtaining archival tumor tissue [OPTIONAL] – this can occur anytime during or after the Screening visit
10. Tumor biopsy and/or FDG-PET scan [OPTIONAL].
11. For patients in the malignant effusion Extension cohort, recording of the number of effusion removal procedures and volume, if appropriate (e.g. paracentesis or thoracentesis) required over the previous 6 months.
12. For the GIST cohort, tumor genotyping results for Kit and PDGFR from a CLIA-certified laboratory should be provided if available.

13. For patients enrolled after the implementation of Amendment 8, dispense six (6) Numeric Rating Scale (NRS) for PVNS Symptoms questionnaires with instructions and reminders to complete the daily questionnaire on an outpatient basis for the 6 consecutive days (Day -6 to Day -1) prior to the next scheduled study visit on C1D1 and to bring the completed questionnaires back at that visit. NOTE: At each of the applicable visits, sites should refrain from providing any interpretation of how the questions should be answered by the patient.

A patient who meets all of the inclusion criteria will be assigned a patient number. Each patient should fast for 1 hour before and 1 hour after test article administration.

14.2 Pre-Treatment (Baseline): Cycle 1 Day 1

Patients will return to the clinic on C1D1 and will undergo the following procedures:

1. Recording of concomitant medications.
2. Vital signs (sitting blood pressure, pulse rate, and respiratory rate and oral temperature [$^{\circ}$ F]).
3. Pre-dose blood sample collection for PK analysis and response biomarkers.
4. Pre-dose morning (second void, between approximately 7 AM and 10 AM) urine collection for response biomarkers.
5. For patients enrolled after the implementation of Amendment 8, collect the six (6) completed NRS for PVNS Symptoms questionnaires and give the patient another one of the questionnaires to complete predose. NOTE: the NRS for PVNS Symptoms questionnaire to be completed in the clinic is exactly the same as the other 6 daily questionnaires.
6. For patients enrolled after the implementation of Amendment 8, then give the patient the Western Ontario and McMaster Universities Osteoarthritis Index (WOMAC) questionnaire to complete predose. NOTE: At each of the applicable visits, sites should refrain from providing any interpretation of how the questions should be answered by the patient.

14.3 Post-Treatment: Cycle 1 Day 1

On C1D1, each patient will receive the assigned dose of test article. AE monitoring will be continuous.

14.4 Cycle 1 Day 15 (\pm 2 days)

At the C1D15 visit, AEs, concomitant meds, vital signs, physical exam, test article compliance, and clinical laboratory values will be recorded. An ECG will be obtained, and PK blood samples

will be obtained predose (AM) and at 1, 2, 4 and 6 hours postdose (for patients who have an afternoon clinic visit, the documentation of dosing and PK sampling times is described in [Section 20.1](#)). If obtained at the pre-dose Baseline, a repeat tumor biopsy and/or FDG-PET scan may be obtained.

For patients enrolled after the implementation of Amendment 8, give the patient the NRS for PVNS Symptoms questionnaire to complete predose. Then give the patient the WOMAC questionnaire to complete predose. Then dispense six (6) NRS for PVNS Symptoms questionnaires with instructions and reminders to complete the daily questionnaire on an outpatient basis for the 6 consecutive days (Day -6 to Day -1) prior to the C2D1 study visit and to bring the completed questionnaires back at that visit.

14.5 Cycle 2 Day 1 (\pm 7 days)

On C2D1, evaluations will consist of AEs, concomitant meds, compliance, physical exam with vital signs, weight, ECOG performance status assessment, clinical laboratory values, a predose PK time-point, and serum/urine collection for biomarkers.

For patients enrolled after the implementation of Amendment 8, collect the six (6) completed NRS for PVNS Symptoms questionnaires and give the patient another one of the questionnaires to complete predose. Then give the patient the WOMAC questionnaire to complete predose. Once all other C2D1 procedures have been completed, dispense six (6) NRS for PVNS Symptoms questionnaires with instructions and reminders to complete the daily questionnaire on an outpatient basis for the 6 consecutive days (Day -6 to Day -1) prior to the next scheduled study visit and to bring the completed questionnaires back at that visit.

14.6 Continued Dosing

14.6.1 Visits through Cycle 40

Pexidartinib, at the assigned dose, will be offered to each patient as long as both the patient and investigator agree that it continues to be well tolerated, and there has been no evidence of disease progression. Study visits will occur at 4-week (\pm 7 days) intervals for assessment of safety (AEs, concomitant meds, physical exam with weight and vital signs, PK, and clinical laboratory values), compliance, and ECOG status, and 8-week intervals (or as clinically indicated) for radiographic assessment of tumor response or progression. Radiographic assessment of tumor status can be performed every four cycles in patients who complete 15 cycles of treatment and have Cycle 13 and Cycle 15 MRI scans that indicate SD or better per local RECIST v1.1 reading (cycle 19, 23, 27...). For PVNS patients, the Sponsor will receive radiologic images for possible retrospective analysis of treatment response, to be performed by a central vendor. For the malignant effusion cohort, the frequency and volume of on-study fluid removal procedures should be recorded.

For patients enrolled after the implementation of Amendment 8, every four weeks collect the six (6) completed NRS for PVNS Symptoms questionnaires and give the patient another one of the questionnaires to complete predose. Then give the patient the WOMAC questionnaire to complete predose. Once all other procedures have been completed at the visit, dispense six (6) NRS for PVNS Symptoms questionnaires with instructions and reminders to complete the daily questionnaire on an outpatient basis for the 6 consecutive days (Day -6 to Day -1) prior to the next scheduled study visit 4 weeks later and to bring the completed questionnaires back at that visit.

14.6.2 Visits after Cycle 40

Pexidartinib, at the assigned dose, will be offered to each patient as long as both the patient and investigator agree that it continues to be well tolerated, and there has been no evidence of disease progression. Study visits will occur at 12-week (± 7 days) intervals (i.e., every 3 cycles) for assessment of safety (AEs, concomitant meds, physical exam with weight and vital signs, hematology, and chemistry), compliance, and 24-week intervals (i.e., every 6 cycles, or as clinically indicated) for radiographic assessment of tumor response or progression. For patients without ongoing Grade 2 or greater related adverse events, frequency of on-site visits may be extended to every 24 weeks, with remote serum chemistry and hematology as well as a telephone check-in for AEs and con meds and to review remote safety laboratory data performed 12 weeks after each on-site visit; Weight, PE, Vitals, WOMAC, NRS, and IP compliance will not be performed remotely). For PVNS patients, the Sponsor will receive radiologic images for possible retrospective analysis of treatment response, to be performed by a central vendor.

At every on-site visit the six (6) completed NRS for PVNS Symptoms questionnaires will be collected and the patient will be given another one of the questionnaires to complete predose. Then the patient will be given the WOMAC questionnaire to complete predose. Once all other procedures have been completed at the visit, six (6) NRS for PVNS Symptoms questionnaires will be given to the patient with instructions and reminders to complete the daily questionnaire on an outpatient basis for the 6 consecutive days (Day -6 to Day -1) prior to the next scheduled study visit 12 weeks later and to bring the completed questionnaires back at that visit.

14.7 Dose Modification (Extension Cohorts)

Reduction/interruption of dosing for adverse events may take place at any time during the study according to guidelines in [Table 3](#). Dose reductions should occur in increments of 200 mg/day, depending on the toxicity grade, as noted in [Table 3](#). Dose reduction/interruption guidelines for hematologic and nonhematologic treatment-related TEAEs are based on severity. Dose interruptions can be implemented at the discretion of the treating Investigator to manage intolerable or clinically significant toxicity. If a dose interruption is required, study assessments should be performed as scheduled, irrespective of the study drug delay, with the exception of PK assessments, which should be deferred until treatment is resumed. Interruptions due to toxicity

lasting >3 weeks require treatment discontinuation unless the medical monitor approves continuation.

Table 3: Dose Modifications

Event	Severity	Pexidartinib Dosage Modifications
Hepatotoxicity		
Increased ALT and/or AST	>3 to 5 × ULN	Withhold and monitor liver tests weekly. If AST and ALT ≤3 × ULN within 4 weeks, resume at reduced dose. If AST or ALT not ≤3 × ULN in 4 weeks, permanently discontinue pexidartinib.
	>5 to 10 × ULN	Withhold and monitor liver tests twice weekly. If AST and ALT ≤3 × ULN within 4 weeks, resume at reduced dose. If AST or ALT not ≤3 × ULN in 4 weeks, permanently discontinue pexidartinib.
	>10 × ULN	Permanently discontinue pexidartinib. Monitor liver tests twice weekly until AST or ALT ≤5 × ULN, then weekly until ≤3 × ULN.
Increased ALP ^a and GGT	ALP >2 × ULN with reflex test of GGT >2 × ULN	Permanently discontinue pexidartinib. Monitor liver tests including GGT twice weekly until ALP ≤5 times ULN, then weekly until ≤2 × ULN.
Increased bilirubin	TB >ULN to <2 × ULN or DB >ULN and <1.5 × ULN	Withhold and monitor liver tests twice weekly. If an alternate cause for increased bilirubin is confirmed and bilirubin <ULN within 4 weeks, resume at reduced dose. If bilirubin not <ULN in 4 weeks, permanently discontinue pexidartinib.
	TB ≥2 × ULN or DB >1.5 × ULN	Permanently discontinue pexidartinib. Monitor liver tests twice weekly until bilirubin ≤ULN.
Adverse Reactions or Other Laboratory Abnormalities		
Any	Severe or intolerable	Withhold until improvement or resolution. Resume at a reduced dose upon improvement or resolution.

ALT = alanine aminotransferase; ALP = alkaline phosphatase; AST = aspartate aminotransferase;
DB = direct bilirubin; GGT = gamma-glutamyl transferase; TB = total bilirubin; ULN = upper limit of normal

^a Confirm ALP elevations as liver isozyme fraction.

Dose interruptions for Grade 2 non-hematologic toxicity for up to 1 week can be implemented at the discretion of the treating physician to manage intolerable or clinically significant toxicity. No dose reduction is required when resuming treatment.

Liver enzyme abnormalities, including increased transaminase values, have occurred with pexidartinib and should also be managed as described in [Table 4](#).

Re-challenge with a reduced dose of pexidartinib may result in a recurrence of increased serum transaminases, bilirubin, or ALP. Monitor liver tests weekly for the first month after re-challenge.

Table 4: Additional Liver Evaluation

Evaluation	Comments
Increase frequency of testing liver chemistries to twice per week (if Grade 3+), including INR, and continue until liver chemistries have stabilized, and then reduce to weekly until liver chemistries return to normal or baseline.	Investigational treatment may be started after liver function tests recover to Grade 0 to 1 or baseline level, and in consultation with Medical Monitor.
Detailed history focusing on medications and substances used: alcohol, change in medication dosages, new medications added, attention to use of acetaminophen, OTC medication use, and recreational drug use. Check for change in diet or use of dietary supplements, with particular attention to dose and duration of any herbal product.	Suspect medications will be discontinued or substituted for if possible.
Detailed medical history and physical examination seeking new abnormalities.	Evaluate abnormalities found.
Full serological evaluation for hepatitis A, B, C, and E (IgG and IgM). Check for autoimmune hepatitis with serological laboratory studies.	If viral hepatitis or autoimmune hepatitis suggested, have patient evaluated by hepatologist.
Liver ultrasound performed to evaluate liver and biliary tree.	Evaluate any abnormalities found.
Check history for exposure to chemical agents.	Remove chemical exposure and have patient seen by hepatologist.
Obtain hepatology consult if liver function continues to rise beyond 14 days.	Contact Medical Monitor.
We request that cases be discussed with the Medical Monitor as defined in the protocol whenever investigational product is being held for liver function test abnormality.	

Ig = Immunoglobulin; INR = international normalized ratio; OTC = over-the-counter

For suspected cases of cholestatic liver injury (e.g., aminotransferase increase concurrent with hyperbilirubinemia, or liver biopsy suggesting cholestasis and/or ductopenia), patients will be followed to assess long-term outcome. Additional diagnostic and follow-up procedures might be implemented as appropriate to fully assess the event.

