5. All associated toxicity from previous or concurrent cancer therapy must be resolved (to \leq Grade 1 or Baseline) prior to administration of pexidartinib.

6. Willing and able to provide written informed consent prior to any study related procedures and to comply with all study requirements.
7. ECOG performance status 0 or 1.
8. Life expectancy ≥ 3 months.
9. Adequate hematologic, hepatic, and renal function (absolute neutrophil count $\geq 1.5 \times 10^9/L$, Hgb >9 g/dL, platelet count $\geq 100 \times 10^9/L$, AST/ALT $\leq 2.5 \times$ ULN or $<5 \times$ ULN in the presence of liver metastases, albumin ≥ 3 g/dL, creatinine $\leq 1.5 \times$ ULN or calculated CrCl >60 mL/min using Cockcroft-Gault formula).

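### Extension cohorts: entry criterion 9, the 14.7 lead-in, Table 3 and Table 4 give conflicting instructions for a patient whose liver tests were already raised at baseline

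*Combined protocol and SAP*

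**What the plan says.** **Entry.** Criterion 9 (Section 10.1, repeated in the Synopsis) asks for "Adequate hematologic, hepatic, and renal function". Its hepatic components are AST/ALT no higher than 2.5 × ULN, or below 5 × "ULN in the presence of liver metastases", and a minimum albumin. It gives no figure for bilirubin, ALP or GGT, and the exclusion criteria in Section 10.2 add none.

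**Action levels.** Table 3 (Section 14.7, Extension cohorts) is written in absolute multiples of ULN.
- AST/ALT above 3 and up to 10 × ULN (two rows): withhold, then "If AST or ALT not ≤3 × ULN in 4 weeks, permanently discontinue pexidartinib". Above 10 × ULN: permanent discontinuation at once.
- Bilirubin, lower row, "TB >ULN to <2 × ULN or DB >ULN and <1.5 × ULN": withhold, then "If bilirubin not <ULN in 4 weeks, permanently discontinue pexidartinib". Bilirubin, upper row (TB from 2 × ULN or DB above 1.5 × ULN): permanent discontinuation.
- "ALP >2 × ULN with reflex test of GGT >2 × ULN": permanent discontinuation, with a footnote requiring the ALP rise to be confirmed as the liver isozyme.

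No row mentions the baseline value.

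**Text pointing the other way.** The paragraph introducing Table 3 speaks of dosing changes for adverse events and of guidelines for treatment-related TEAEs. Table 4, which the section says also governs liver enzyme abnormalities, states: "Investigational treatment may be started after liver function tests recover to Grade 0 to 1 or baseline level". It adds that this is done in consultation with the Medical Monitor.

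**The concern.** The entry limits and the action levels overlap, and the two tables treat a raised baseline differently. A site holding such a patient's dose can find an instruction to stop permanently and, in the next table, permission to restart. Two sites could each follow the protocol and act in opposite ways on a liver stopping rule. What is at stake is even application of that safeguard, and a clear meaning for any hepatic discontinuation recorded in a patient whose value is no worse than at entry.

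**Working it through.** The plan states no figure on this point, so the check sets the passages side by side.

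**Step 1: overlap between entry limits and Table 3.**

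| Test | Permitted at entry | Table 3 level reached within that range |
|---|---|---|
| AST/ALT, no liver metastases | ≤2.5 × ULN | None (lowest trigger is >3 × ULN) |
| AST/ALT, liver metastases | <5 × ULN | Values >3 and <5 × ULN: lowest withhold row only |
| Bilirubin | No numeric limit | Both rows, including immediate permanent discontinuation |
| ALP with GGT | No numeric limit | Permanent discontinuation row |

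No permitted AST/ALT value reaches the row above 5 × ULN or the row above 10 × ULN. For AST/ALT, permanent discontinuation can therefore follow from the entry value only through the 4-week step.

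**Step 2: where Tables 3 and 4 diverge.** The Extension flow chart footnotes and Attachment 1 equate Grade 2 or higher AST/ALT with >3 × ULN. Grade 0 to 1 is then ≤3 × ULN, which is Table 3's recovery target. For a patient with baseline ≤3 × ULN the baseline alternative in Table 4 adds nothing, and the two tables share a recovery level. They part only when baseline is above 3 × ULN, which is the band found in Step 1.

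**Step 3: a worked patient.** Liver metastases; AST 4 × ULN at entry (4 < 5, eligible); rises on drug to 8 × ULN; returns to 4 × ULN and stays there.
- Table 3: 8 lies in the >5 to 10 row, so withhold. At 4 weeks AST is 4 × ULN, and 4 > 3, so permanent discontinuation.
- Table 4: 4 × ULN is the baseline level, so treatment may be started in consultation with the Medical Monitor.

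The conflict does not depend on the 8. Any peak above 4 and up to 10 × ULN gives it. Nor does it depend on attribution, because the rise here may be a genuine treatment-related TEAE and so fall within the lead-in.

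**Step 4: bilirubin.** The lower bilirubin row allows resumption only if an alternate cause is confirmed **and** bilirubin is below ULN within 4 weeks. If it is not below ULN, the patient is permanently discontinued even with another cause confirmed. This sits uneasily with a lead-in directed at treatment-related events.

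**Step 5: unchanged baseline.** Read alone, the Table 3 cells also catch a patient whose entry value never moves. With AST steady at 4 × ULN, the first scheduled on-treatment chemistry (C1D15) puts the patient in the withhold row, and the 4-week limit falls at day 15 + 28 = day 43. The lead-in points against that reading, because a value that has not changed is not treatment-emergent.

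**The case against.** **Scope.** The strongest reply is that Section 14.7 offers guidelines for adverse events and treatment-related TEAEs. The liver rows sit under a hepatotoxicity heading and are labelled as increases. Section 26.1 lists worsening of a pre-existing condition as an adverse event, and a stable value has not worsened. This stands against one inference a reader might draw, that an eligible patient must be stopped with no change from baseline. The documents support that only if the Table 3 cells are read without their introduction and without Table 4. It does not answer Step 3, where the event is treatment-emergent. The lead-in sentence also covers reduction and interruption without mentioning permanent discontinuation.

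**Precedence.** Table 4 is permissive and involves the Medical Monitor, so a site could satisfy both tables by applying the stricter one. Nothing says Table 3 prevails, however. If it did, Table 4's baseline alternative would have no effect for AST/ALT (Step 2). The restart comment also sits beside a testing instruction for Grade 3 or higher, and the text does not say whether it is confined to such cases. The lead-in separately makes interruptions for toxicity beyond 3 weeks end in discontinuation unless the medical monitor approves continuation. Table 3's 4-week step carries no such exception.

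**Eligibility.** A missing bilirubin or ALP/GGT figure is not a grant of eligibility. Criterion 9 still requires adequate hepatic function, and exclusion 6 leaves room for investigator judgement. This stands: that part of the overlap is an absent limit, not a stated one.

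**Benefit count.** A reader might also infer that such patients would distort the 2-of-10 clinical benefit rule in Section 24.6. With last dose near day 15, the 12-week follow-up scan falls at day 15 + 84 = 99, or 127 with its 28-day window, short of about day 182 for 6 months. But Section 14.9 accepts scans from any source within 24 weeks of last dose for patients who miss follow-up (15 + 168 = day 183). Section 24.2 censors PFS at the last evaluable assessment, not at treatment stop. No rule counts these patients as failures, and no frequency is given. The inference is not supported.

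**Safety data.** Attachment 1 lists AST, ALT, ALP and bilirubin, chemistry is drawn at screening, and Section 24.1 plans changes from baseline. Pre-existing and emergent values can largely be separated. Only GGT is not listed.

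**Conclusion.** The point holds as an internal contradiction in the Extension cohorts. The dose escalation cohorts follow Section 13.9 and are not affected.

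For AST/ALT it is confined to patients with liver metastases who enter above 3 and below 5 × ULN, and at entry it reaches only the lowest withhold row. In that band, after a rise to no more than 10 × ULN and a return to baseline, Tables 3 and 4 give opposite instructions, and the lead-in does not settle which applies. For bilirubin and ALP/GGT, Table 3 levels up to immediate permanent discontinuation can be met at entry because no numeric limit is stated, subject to the general requirement for adequate hepatic function.

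The conclusion rests on reading the tables as printed and on the protocol's own equation of Grade 2 or higher AST/ALT with >3 × ULN. The number of patients affected cannot be derived from the documents. It does not extend to a forced stop for every patient with an unchanged baseline elevation, nor to any quantified effect on the benefit rule.

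**What to change.** Reconcile criterion 9 (Section 10.1 and the Synopsis), the 14.7 lead-in, Table 3 and Table 4 so that together they give one instruction for a patient whose liver tests were already elevated at entry. The text should make clear:
- whether the Table 3 liver rows apply to a pre-existing value;
- what counts as recovery for such a patient;
- which table governs when the two differ;
- how the bilirubin row works when an alternate cause is confirmed.

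The 3-week provision in the lead-in and the 4-week step in Table 3 should be aligned in the same pass. Which passage changes, and to what, is for the sponsor to decide; no threshold is proposed here.

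The cost is amendment wording. The reconciliation does not in itself alter the sample size, the visit schedule or the planned analyses. If the sponsor chose to change criterion 9, the set of eligible patients could shift, and it would need to weigh that.
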